#### 8.0 STATISTICAL ANALYSIS:

We are proposing a single arm, single center open label trial to assess the safety and tolerability of defibrotide for patients with SARS-CoV2 induced ARDS.

# 8.1 Primary study endpoint

The primary safety endpoint will be the occurrence of major toxicity, specifically hemorrhagic complications within 14 days of initiation of treatment.

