# 6.4 Criteria to Hold Study Therapy

Study drug will be held in the following settings:

Patients who develop signs of "major bleeding" as defined by International Society on Thrombosis and Haemostasis (ISTH) criteria (Appendix 3), will have defibrotide held at that time.

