#### Additional criteria:

- In addition, defibrotide therapy will be held if symptomatic alveolar hemorrhage, macroscopic hematuria, uncontrolled menorrhagia (i.e. requiring therapy), uncontrolled epistaxis (> 10 minutes duration) requiring cauterization and/or nasal packing, or uncontrolled bleeding from a wound site (i.e. bleeding requiring therapeutic intervention) occur.
- Blood tinged endotracheal secretions, microscopic hematuria, mild menorrhagia, and/or epistaxis < 10 minutes duration do not require withholding of drug therapy unless the treating medical team deems that the event requires direct medical intervention.

Therapy may resume once the bleeding diathesis has been resolved for at least 24 hours, and may be restarted at the same dose and dosing schedule. If any further signs of bleeding develop upon re-initiation of therapy, defibrotide would be discontinued and not re-started. Patients who develop signs of CNS hemorrhage or diffuse alveolar hemorrhage

should discontinue study therapy immediately, and will not resume therapy at any time point.

Defibrotide will be held for surgical procedures or to accommodate other urgent intervention (central line placement) without necessitating dose modification. For surgical procedures it is recommended that defibrotide administration be completed > 2 hours prior to the procedure. The DF may be resumed 24 hours after completion of the procedure (or later) based upon the clinical discretion of the treating physician.

In situations in which defibrotide therapy was temporarily held and then resumed, no additional doses of defibrotide will be given to account for any doses that were missed while the drug was being held.

Defibrotide will be discontinued permanently for the development of a "severe or life-threatening (anaphylaxis) hypersensitivity reaction.

Defibrotide will be discontinued permanently if a patient initiates extra-corporeal membrane oxygenation (ECMO) therapy for any reason.

Defibrotide dosing for acute hypersensitivity reactions is discussed in section 6.5 below.

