# 8.3 Primary stopping rule

An incidence of > 20% hemorrhagic complications would be unacceptable in this setting. Thus, we will continually monitor the observed proportion of patients with major bleeding complications. We start with prior Beta(2,8) distribution, which has mean 0.2. If ever we have more than 80% posterior probability that the true proportion is greater than 0.20,

accrual to the protocol will be suspended to allow the DSMB to review the incidence of major bleeding.

Specifically, if we see at least **three** patients with major bleeding among the first six patients, or at least **four** patients with major bleeding among the first eleven patients, the study will be suspended. If the true proportion of major bleeding events is 0.20, the study has a probability of 0.19 of being suspended. If the true proportion of major bleeding events is 0.30 or 0.40, the probability of trial suspension is 0.47 and 0.73, respectively. Note that if the trial is suspended to accrual, the accrual is expected to be seven patients.

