# 8.4 Secondary endpoints

There are two secondary endpoints: (i) Day 14 overall survival and (ii) Day 14 ventilator-free survival, both of which are binary endpoints. Day 14 overall survival will be summarized by the proportion of the twelve patients who are alive at Day 14 after starting treatment, and Day 14 ventilator-free survival will be summarized by the proportion of the twelve patients who are both alive and not using a ventilator at Day 14 after starting treatment. Both proportions will be accompanied by an exact 95% confidence interval.

We will also continually monitor the study for excessive Day 14 mortality. In parallel with our decision rule related to excessive severe hemorrhagic events, we will suspend accrual if we see if we see at least five deaths by Day 14 among the first six patients, or at least seven deaths by Day 14 among the first eleven patients. If the true Day 14 mortality rate is 70% (which is the historical rate for patients with respiratory comprise), the study has a probability of 0.80 of being suspended. Conversely, if the Day 14 mortality rate is 50%, the study has a much lower probability of 0.30 of being suspended.

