# 9.0 OFF STUDY CRITERIA

Defibrotide will be discontinued for any of the following reasons:

- Withdrawal of consent / patient choice.
- The patient experiences an adverse event which, in the opinion of the Investigator, contraindicates continuation in the study.
- Protocol violation, including disallowed concomitant therapy.
- The Investigator considers it not in the patient's best interest to continue.
- Defibrotide-related toxicity (including hemorrhage as defined in section 6.4)
- Subject death.

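### The primary endpoint and the 20% limit are stated for hemorrhagic complications but the suspension rule counts major bleeding, so a serious alveolar hemorrhage may be left out of the count

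*Combined protocol and SAP*

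**What the plan says.** Section 8 describes the bleeding event in several ways.

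- 8.1, primary endpoint: "The primary safety endpoint will be the occurrence of major toxicity, specifically hemorrhagic complications within 14 days of initiation of treatment".
- 8.3, unacceptable rate: "An incidence of > 20% hemorrhagic complications would be unacceptable in this setting".
- 8.3, monitored quantity: "we will continually monitor the observed proportion of patients with major bleeding complications". The 3-in-6 and 4-in-11 boundaries and the stated suspension probabilities are also given for major bleeding.
- 8.4, referring back to the same rule: "In parallel with our decision rule related to excessive severe hemorrhagic events".

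None of these sections cites a definition, and only 8.1 gives a time window for bleeding.

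Major bleeding is defined elsewhere, for the drug-hold rule. Section 6.4 takes it "as defined by International Society on Thrombosis and Haemostasis (ISTH) criteria (Appendix 3"). For non-surgical patients Appendix 3 counts three things: fatal bleeding; symptomatic bleeding in a critical area or organ, with examples that do not include the lung; and bleeding with a hemoglobin fall of at least 2.0 g/dl leading to transfusion of two or more units. Every other bleed is minor.

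Under a separate list of additional criteria, 6.4 says "defibrotide therapy will be held if symptomatic alveolar hemorrhage, macroscopic hematuria, uncontrolled menorrhagia" or certain other bleeds occur. For permanent discontinuation it groups two sites: "Patients who develop signs of CNS hemorrhage or diffuse alveolar hemorrhage". Section 10.6 makes pulmonary hemorrhage a protocol-defined serious adverse event when it is judged potentially life-threatening.

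**The concern.** The trial has one primary endpoint, at most 12 patients, and one bleeding rule to protect them. If the endpoint covers hemorrhagic complications and the rule covers Appendix 3 major bleeding, the two can give different counts in the same patients. The 20% limit is then worded for one event and tested on another.

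The bleed most exposed to this is alveolar hemorrhage. The protocol treats its diffuse form as seriously as CNS hemorrhage, and every enrolled patient already has injured lungs. In the Section 13 label data it is the most frequent listed grade 4-5 bleed (12 of 176) and the only bleed among the most common serious reactions (7%). At stake is whether such a bleed moves the trial towards suspension, and whether it appears in the primary result. One patient reclassified out of 12 moves the reported rate by 1/12, or 8.3 percentage points.

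**Working it through.** **Inputs (8.3).** Prior Beta(2,8); accrual is suspended if the posterior P(rate > 0.20) exceeds 0.80; explicit boundaries of at least 3 of the first 6 or at least 4 of the first 11; stated suspension probabilities 0.19, 0.47 and 0.73 at true rates 0.20, 0.30 and 0.40.

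**Step 1: reproduce the plan's figures.** Counts can only rise and each boundary is constant over its span. With X6 and X11 the numbers of events among the first 6 and 11 patients, the suspension probability is

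P(X6 ≥ 3) + Σ over j = 0, 1, 2 of P(X6 = j) × P(Bin(5, p) ≥ 4 − j).

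At p = 0.20: 0.0989 + (0.2621 × 0.0067 + 0.3932 × 0.0579 + 0.2458 × 0.2627) = 0.0989 + 0.0891 = 0.188.

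| True rate | By patient 6 | After patient 6 | Total | Plan |
|---|---|---|---|---|
| 0.20 | 0.099 | 0.089 | 0.188 | 0.19 |
| 0.30 | 0.256 | 0.206 | 0.462 | 0.47 |
| 0.40 | 0.456 | 0.270 | 0.725 | 0.73 |

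The rule's arithmetic is sound. The open question is which event feeds it.

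**Step 2: effect of one classification.** With k events in n patients the posterior is Beta(2 + k, 8 + n − k), and P(rate > 0.20) = P(Bin(n + 9, 0.20) ≤ k + 1). For 3 of 6 this is P(Bin(15, 0.20) ≤ 4) = 0.836.

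| Patients | Alveolar bleed not counted | Alveolar bleed counted |
|---|---|---|
| 4 | 2 events: 0.747 | 3 events: 0.901 |
| 6 | 2 events: 0.648 | 3 events: 0.836 |
| 8 | 3 events: 0.758 | 4 events: 0.894 |
| 11 | 3 events: 0.630 | 4 events: 0.804 |

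In each row the decision to count one bleed moves the posterior across 0.80. The rows are chosen because they lie at the boundary; away from it, one bleed changes nothing.

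**Step 3: illustration of scale.** Suppose a share s of the intended events goes uncounted. The counted rate is then p(1 − s), and the Step 1 formula applies. The documents give no value for s; 10% to 20% is an assumption.

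| True rate | s = 0 | s = 10% | s = 20% |
|---|---|---|---|
| 0.20 | 0.19 | 0.14 | 0.10 |
| 0.30 | 0.46 | 0.37 | 0.29 |
| 0.40 | 0.73 | 0.63 | 0.52 |

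**Step 4: do the definitions allow the omission?** A symptomatic alveolar hemorrhage that is not fatal and does not meet the hemoglobin/transfusion criterion can be major only through the critical-site criterion. The lung is not named there, and 6.4 places this bleed outside its ISTH list. Appendix 3 also gives a bleed that leads to interruption or discontinuation of study drug as an example of a clinically relevant minor bleed. Classing it as minor is therefore permitted by the text, but not compelled.

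**The case against.** The strongest reply is that major bleeding is a defined term. Section 6.4 ties it to Appendix 3, and 8.3 uses it for the monitored quantity, the boundaries and the operating characteristics. That is a fair reading of the rule, but it is the reading under which this bleed may be left out, and it does not reconcile the rule with 8.1 or with the wording of the 20% limit. If Appendix 3 alone was intended throughout, the stated operating characteristics stand for that event, and the reductions in Step 3 apply only to the wider one.

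A reader might infer that alveolar hemorrhage is excluded outright. The documents do not support that: the site list is open, an adjudicator could treat the lung as a critical organ, and fatal or sufficiently transfused alveolar bleeds already count. For the same reason the 12 of 176 is not a count of missed events. It also comes from transplant patients with hepatic veno-occlusive disease, and Section 4 reports similar pulmonary hemorrhage rates in the defibrotide and control groups of the licensing trial (11.8% and 15.6%).

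A reader might also take Section 9, "Defibrotide-related toxicity (including hemorrhage as defined in section 6.4"), as a rival endpoint definition. That is weak: it lists reasons to stop drug and does not mention the endpoint, and its scope would bring in packed epistaxis and treated menorrhagia.

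Oversight is real. There are general and protocol-defined serious adverse event criteria, a monthly committee that can recommend suspension, and DSMB meetings quarterly, after six patients, and more often if needed. These make the bleed visible but do not put it in the count. At a true rate of 0.30, 0.206 of the 0.462 suspension probability (45%) arises after patient six.

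**Conclusion.** The concern holds as a mismatch of definitions, not an error of calculation. Sections 8.1 and 8.3 do not name the same event, and the plan lets the suspension count omit a non-fatal alveolar hemorrhage that the protocol elsewhere treats as serious. When the count is near the boundary, that single omission decides whether the rule fires. How often this would happen cannot be known from the documents, so the Step 3 reductions illustrate scale and do not estimate a loss. A reader might infer that the trial could run on unsafely unnoticed. The documents do not support that, since the bleed would be seen through adverse event reporting, and crossing the boundary only suspends accrual for DSMB review. The point should be fixed before the count is used, with medium confidence as to its practical effect.

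**What to change.** Reconcile 8.1, 8.3, 8.4, 6.4, 10.6 and Appendix 3 so that one named, cross-referenced event, from first dose to Day 14, serves as the primary endpoint, the event for the 20% limit and the stopping event. Count symptomatic alveolar or pulmonary hemorrhage in it together with Appendix 3 major bleeding. Confirm that the 20% limit and the Beta(2,8) prior are meant for that event. Report Appendix 3 major bleeding alone as a supporting count.

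The cost is mainly protocol wording. Adverse events are assessed daily on therapy, and for 7 days afterwards while the patient is in hospital. Symptomatic alveolar hemorrhage also triggers a drug hold, so existing records should already capture it. The downside is a somewhat higher reported rate and a higher chance of suspension for DSMB review. If 20% of events were otherwise uncounted (an assumption), the suspension probability rises from 0.014 to 0.027 at a true rate of 0.10 (counted rate 0.10 × 0.8 = 0.08), and from 0.10 to 0.19 at a true rate of 0.20 (counted rate 0.20 × 0.8 = 0.16).

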# 8.2 Sample size justification

This study is intended to be a feasibility study of potential hemorrhagic complications associated with defibrotide in our study population. Thus, this study will enroll a maximum of **twelve patients**, which is the number of patients that we can expect to accrue in the current setting of the SARS-CoV2 pandemic.

# 8.3 Primary stopping rule

An incidence of > 20% hemorrhagic complications would be unacceptable in this setting. Thus, we will continually monitor the observed proportion of patients with major bleeding complications. We start with prior Beta(2,8) distribution, which has mean 0.2. If ever we have more than 80% posterior probability that the true proportion is greater than 0.20,

accrual to the protocol will be suspended to allow the DSMB to review the incidence of major bleeding.

Specifically, if we see at least **three** patients with major bleeding among the first six patients, or at least **four** patients with major bleeding among the first eleven patients, the study will be suspended. If the true proportion of major bleeding events is 0.20, the study has a probability of 0.19 of being suspended. If the true proportion of major bleeding events is 0.30 or 0.40, the probability of trial suspension is 0.47 and 0.73, respectively. Note that if the trial is suspended to accrual, the accrual is expected to be seven patients.

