# 11.0 DATA SAFETY MONITORING:

Protocol Monitoring Committee: A protocol monitoring committee consisting of the principal investigators, one or more co-investigators, study coordinator, and data manager will meet monthly during the conduct of the study to discuss expected and unexpected adverse events, safety concerns, adherence to protocol therapy, study enrollment, and any potential protocol amendments that may be required. Recommendations for study continuation, amendments, suspension and/or study termination will be made at each of the monthly protocol monitor meetings and formally submitted to an independent Data Safety Monitoring Board.

Data Safety Monitoring Board (DSMB): Membership shall consist of two external (non-Michigan Medicine) and two internal (Michigan Medicine) physicians. The DSMB will be an independent body, with none of the DSMB members serving as study co-investigators. The DSMB will meet quarterly to review the conduct of the study, including review of all monthly reports submitted from the protocol monitoring committee. More frequent DSMB meetings may be required, pending any issues raised in the monthly reports from the protocol monitoring committee. In addition, the DSMB will review the study after the first 6 patients have completed study drug therapy, to determine if the study stopping rules for early termination have been met, and if the study enrollment should be terminated or allowed to continue. Enrollment will be held once the 6th patient has completed study drug therapy, to allow the DSMB to make this determination. Reports from the DSMB meetings will be furnished to IRBMED in accordance with Michigan Medicine policies.

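### The printed bleeding counts in Section 8.3 leave out one trigger that the stated 80% posterior rule requires: two events in the first two patients

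*Combined protocol and SAP*

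**What the plan says.** Section 8.3 defines the bleeding rule in two steps.

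The first step is a Bayesian criterion. The prior is given as "We start with prior Beta(2,8) distribution, which has mean 0.2", the plan says "we will continually monitor the observed proportion of patients with major bleeding complications", and accrual is suspended for DSMB review "If ever we have more than 80% posterior probability that the true proportion is greater than 0.20". No minimum number of patients is set before the criterion applies.

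The second step, introduced as the specific form of the first, is a pair of counts: at least three "patients with major bleeding among the first six patients, or at least" four among the first eleven.

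The operating characteristics follow: "If the true proportion of major bleeding events is 0.20, the study has a probability of 0.19 of being suspended"; at true proportions of 0.30 and 0.40 "the probability of trial suspension is 0.47 and 0.73, respectively". On sample size the plan adds: "Note that if the trial is suspended to accrual, the accrual is expected to be seven patients".

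The Synopsis and Section 11.0 refer to the stopping rules without restating them. Section 11.0 schedules a DSMB review after six patients have completed therapy "to determine if the study stopping rules for early termination have been met". The bleeding boundary is therefore defined only in Section 8.3.

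**The concern.** The counts should be the posterior criterion worked out for each number of patients. If so, every reachable combination of events and patients with a posterior probability above 0.80 should be covered by them. Two events in two patients is not: it is fewer than three events, so neither count is met. A team working from the counts would keep enrolling at a point where the criterion in the same section calls for a pause. Major bleeding is the primary safety endpoint (Section 8.1), and this is the plan's only numerical limit on it.

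**Working it through.** **Inputs, from Sections 8.2 and 8.3.** Prior Beta(2,8); threshold P(p > 0.20) > 0.80; monitoring after every patient; maximum 12 patients; printed counts 3 of 6 and 4 of 11; stated suspension probabilities 0.19, 0.47 and 0.73; stated accrual if suspended, seven.

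**1. The plan's own figures.** The number of events cannot fall, so the counts suspend with probability

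P(X6 ≥ 3) + Σ (x = 0 to 2) P(X6 = x) · P(Y5 ≥ 4 − x),

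where X6 is binomial over the first six patients and Y5 is binomial over the next five.

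- p = 0.20: 0.0989 + (0.2621 × 0.0067 + 0.3932 × 0.0579 + 0.2458 × 0.2627) = 0.0989 + 0.0891 = 0.188.
- p = 0.30 and 0.40, in the same way: 0.462 and 0.725.

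Patient-by-patient enumeration gives the same probabilities, with mean accrual if suspended of 7.4, 7.1 and 6.6. The plan's 0.19, 0.47, 0.73 and seven are thus reproduced to within 0.01 and by rounding.

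**2. The posterior boundary.** After x events in n patients the posterior is Beta(2 + x, 8 + n − x). For integer a and b, P(Beta(a, b) > 0.2) = P(Bin(a + b − 1, 0.2) ≤ a − 1). For 2 of 2 this is Beta(4,8), so P(Bin(11, 0.2) ≤ 3) = 0.8389.

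| Patients n | Fewest events that trigger | Posterior probability at key points | Printed counts trigger at |
|---|---|---|---|
| 1 | none | 1/1: 0.678 | none |
| 2 | 2 | 2/2: 0.8389 | none |
| 3 to 6 | 3 | 2/3: 0.7946; 3/6: 0.8358 | 3 |
| 7 to 11 | 4 | 3/7: 0.7982; 4/11: 0.8042 | 4 |
| 12 | 5 | 4/12: 0.7693; 5/12: 0.8915 | none |

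Five of 12 adds nothing, because any path to it has already had at least four events in 11. The counts and the rule therefore differ only at 2 of 2.

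**3. Consequence of the gap.** From 2 of 2, the counts never suspend only if patients 3 to 6 have no event and patients 7 to 11 have at most one: (1 − p)^4 · P(Bin(5, p) ≤ 1).

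| | p = 0.20 | p = 0.30 | p = 0.40 |
|---|---|---|---|
| P(2 of 2) = p² | 0.04 | 0.09 | 0.16 |
| Never suspended, given 2 of 2 | 0.4096 × 0.7373 = 0.302 | 0.2401 × 0.5282 = 0.127 | 0.1296 × 0.3370 = 0.044 |
| Mean further patients enrolled, given 2 of 2 | 5.2 | 3.7 | 2.7 |
| Increase in P(suspend) if 2 of 2 is added (row 1 × row 2) | 0.012 | 0.011 | 0.007 |

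The third row runs to suspension or patient 12, and assumes that each outcome is known before the next patient enrolls.

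**4. Both versions against the stated figures.**

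| | P(suspend) at 0.20 / 0.30 / 0.40 | Mean accrual if suspended |
|---|---|---|
| Stated | 0.19 / 0.47 / 0.73 | 7 |
| Printed counts | 0.188 / 0.462 / 0.725 | 7.4 / 7.1 / 6.6 |
| Full posterior rule | 0.200 / 0.473 / 0.732 | 6.6 / 6.5 / 6.0 |

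To two decimals, 0.19 agrees only with the counts and 0.47 only with the full rule. Gaps of this size could be rounding or simulation error, so they do not show which version was used.

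**The case against.** The strongest reply is that the governing sentence already covers 2 of 2. The counts are never said to be the only triggers, and a team that follows both sentences would pause. That is a fair reading, but the counts are offered as the specific form of the rule and are what a coordinator would use. The reply reduces the problem to an incomplete list; it does not remove it. A start at the third patient may have been intended, which would make the counts complete, but the plan does not say so.

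Several points on size stand:

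- The gap is brief. One event-free third patient takes the posterior to 0.795, below the threshold.
- The endpoint window is 14 days (Section 8.1) and nothing requires one outcome to be complete before the next enrollment. With overlapping enrollment the trial might never be in a 2-of-2 state, so the further-patient figures could shrink to nothing.
- The largest conditional figures (5.2 further patients, 30% never suspended) apply at a true rate of exactly 0.20. The plan calls only rates above that unacceptable.
- Suspension is a pause for review. Serious events reach the principal investigator within 24 hours (Section 10.7), a committee meets monthly, and extra DSMB meetings are possible (Section 11.0). These would probably bring two early bleeds to light, though none of them requires accrual to stop.

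**Conclusion.** The concern holds, as a minor inconsistency. The printed counts omit exactly one trigger required by the stated criterion, and they do so where the posterior evidence is stronger than at either printed limit. The result rests on the stated prior and threshold, and on reading the criterion as applying from the first patient, which is what the text says. The effect on the design is about one percentage point of suspension probability. The effect in the rare 2-of-2 case is larger, but it depends on outcomes being known one patient at a time. The small differences from the stated probabilities are not a separate error.

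**What to change.** Reconcile the two sentences in Section 8.3 in one of two ways, at the sponsor's choice:

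1. Add two of the first two patients to the printed triggers. The suspension probabilities become 0.20, 0.47 and 0.73. Mean accrual if suspended becomes 6.6, 6.5 and 6.0, so the sentence giving seven also needs changing, since it no longer fits at a true rate of 0.40.
2. State that the posterior criterion applies from the third patient onward. The probabilities become 0.19, 0.46 and 0.73. Mean accrual if suspended is 7.4, 7.1 and 6.6, so seven stands.

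Either way the cost is one clause and one restated probability, plus the accrual figure under the first option. The sample size and the scheduled DSMB review are unaffected.
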